### 9.1 Primary study parameters

At the interim analysis, statistical analyses of the differences in amputation rates between the study arms will be conducted using the Chi-square statistic.

At the final analysis, major amputation rates and AFS will also be estimated using Kaplan-Meier survival analysis and differences between the groups will be analysed using the log-rank test.

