### 3. STUDY DESIGN

Multinational randomized clinical trial with an adaptive (multi-arm, multi-stage; MAMS) design, with a follow-up of 12 months, following the (extended) CONSORT-statement. We will have four study arms and two stages (one interim and one final analysis; see figure 1 below). Patients will be randomized to receive standard treatment with 0, 20, 30 or 40 HBOT treatments.

The more efficient MAMS design (Sydes 2018, Sydes 2012, Wason 2012) for clinical trials includes a planned interim analysis, based on which only the best performing study arms will be chosen to continue. This will reduce the total number of patients required and the number of patients receiving an ineffective treatment, because after the interim analysis no patients will be included in less effective treatment arms.

[figure not shown]

Figure 1 Flow of patient inclusion and analysis

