### 7.2 Randomisation, blinding and treatment allocation

Randomisation will be performed through Castor Electronic Data Capture (Amsterdam, The Netherlands), which also ensures concealed treatment allocation. Stratification will be performed for center and whether or not a patient is included with a minor amputation.

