### 7.3 Study procedures

Patients from each (remaining) study arm will be monitored up to 36 months after randomisation. At the start of the trial, patients' baseline characteristics will be obtained. Pain scores will be collected through first phase of the trial. Questionnaires will be completed at baseline and will be sent to the patients' home after 3 months and 1 year.

Amputation rate, ulcer recurrence, additional interventions, mortality, adverse events and costs will be monitored after 1 year and 3 years.

Assessment	Before randomisation	Week 1-8, once a week	After 3 months	After 1 year	After 3 years
Patient characteristics	*				
Meggitt-Wagner classification	*		*	*	
Wound measurements	*				
Ankle blood pressure	*		*	*	
Toe systolic pressure	*		*	*	
TcPO2	*		*	*	
VAS		*	*	*	
Freedom of amputation			*	*	*
Complete ulcer healing			*	*	*
Recurrent ulcer			*	*	*
Nr of additional vascular events		*	*	*	*
Adverse events		*	*	*	
Patient's out of pocket expenses			*		
Questionnaires	*		*	*	*

*Table 1 Assessments and follow-up*

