### 9.2 Secondary and other study parameters

Differences in (semi-)continuous variables between the two treatment groups (such as the VAS, TcpO2 and quality of life scores) will be analysed with the Student t-test in case of normally distributed data and otherwise the non-parametric Mann-Whitney U test, after correcting for baseline differences, if any.

Time to complete wound healing will be estimated using Kaplan-Meier survival analysis and differences between the groups will be analysed using the log-rank test. Changes over time of TcpO2 and quality of life scores will be analysed using the Wilcoxon test. Potential confounding factors will be adjusted using Cox proportional hazards regression modelling.

The economic evaluation of additional HBOT will be performed as a cost-effectiveness analysis from a societal perspective. Additionally, a cost-utility analysis will be performed with the costs per quality adjusted life-year (QALY) as outcome. As the time horizon is restricted to 12 months, no discounting (of costs and effects) will be performed.

The EQ-5D is used to generate health status scoring profiles over time, which will subsequently be translated in QALYs by applying time trade-off based health utility algorithms and assuming that interpolation between successive measurements best reflects a patient's health status during the year. Sensitivity analyses will be performed to account for sampling variability, for plausible ranges in unit costs, and for different health

utility algorithms. In addition, a budget impact analysis will be undertaken to assess the possible cost savings of HBOT if applied to all eligible patients on a national scale.

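### The stated tests leave out the randomisation strata, make baseline correction depend on the data, and ask for a baseline correction of pain with no pre-randomisation pain score

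*Protocol*

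**What the plan says.** - **Design.** Section 3: "Patients will be randomized to receive standard treatment with 0, 20, 30 or 40 HBOT treatments". That makes four arms.
- **Randomisation.** Section 7.2: "Stratification will be performed for center and whether or not a patient is included with a minor amputation".
- **Primary tests.** At the interim, 9.1 states that "statistical analyses of the differences in amputation rates between the study arms will be conducted using the Chi-square statistic", and 4.4 ties its continuation rules to the same chi-square test. At the final analysis, amputation and amputation-free survival are estimated by Kaplan-Meier and "differences between the groups will be analysed using the log-rank test". Neither place mentions the stratification factors.
- **Continuous outcomes.** Section 9.2 opens with "Differences in (semi-)continuous variables between the two treatment groups (such as the VAS" and goes on to TcpO2 and quality of life. The tests are a t-test or Mann-Whitney test, applied "after correcting for baseline differences, if any". Changes over time in TcpO2 and quality of life get a Wilcoxon test.
- **Other adjustment.** Section 9.2 also provides a Cox model for potential confounders. It names none and does not link the model to the primary tests.
- **Pain schedule.** Section 7.3: "Pain scores will be collected through first phase of the trial". In Table 1 the VAS row is empty before randomisation and marked for weeks 1-8, 3 months and 1 year. TcpO2 and the questionnaires do have a pre-randomisation mark.

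**The concern.** Stratified allocation makes the arms more alike on the stratifying factors than simple randomisation would. If a factor predicts amputation, a test that ignores it uses a standard error too large for the allocation actually made. The interim matters most here, because 68 patients per arm then decide which arms continue.

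For continuous outcomes, three statements do not fit the design:

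- A comparison of two groups does not say which contrasts among four arms are meant.
- Correcting only when a difference appears lets the observed data choose the analysis, and gives up precision in the many trials where baseline looks balanced.
- For VAS, no pre-randomisation value exists to correct with. The earliest score comes after allocation is known. A baseline that was never collected cannot be recovered for patients already enrolled.

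**Working it through.** **The plan's own figures.** 68 × 4 arms × 2 stages = 544, and 544/0.95 = 573. The odds ratios in 4.4 also reproduce: 26% vs 11% gives 0.352 and 26% vs 21% gives 0.757. None of these changes under this point, which concerns precision only.

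**1. Strata and the chi-square test.**

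From the protocol: control risk 26%, one-sided 5%, 68 per arm per stage (136 over two stages). Assumed, because the protocol gives no prognostic strength: two minor-amputation strata of equal size, allocation balanced within each, and stratum odds ratio 2, 4 or 8 with the average risk held at 26%. Centre was not modelled.

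The unstratified test uses variance 0.26 × 0.74 = 0.1924. The variance that applies is ½[a(1−a) + b(1−b)], where a and b are the stratum risks. The true one-sided error is about 1 − Φ(1.645/√ratio).

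| Stratum OR | Risks | Variance ratio | Error, formula | Error, simulated (136/arm) |
|---|---|---|---|---|
| 2 | 19.4% / 32.6% | 0.978 | 4.8% | 4.9% |
| 4 | 13.5% / 38.5% | 0.919 | 4.3% | 4.3% |
| 8 | 8.7% / 43.3% | 0.845 | 3.7% | 3.7% |

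The Mantel-Haenszel test stays at 4.9-5.1% in the same simulations.

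Simulated power of a single pairwise test, unstratified → stratified:

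| Per arm | Comparison | OR 2 | OR 4 | OR 8 |
|---|---|---|---|---|
| 136 | 26% vs 11% | 94.9 → 95.0 | 95.2 → 95.6 | 95.8 → 96.5 |
| 136 | 26% vs 16% | 65.4 → 65.9 | 66.0 → 68.1 | 65.9 → 70.0 |
| 68 | 26% vs 11% | 74.6 → 74.7 | 75.4 → 76.3 | 76.1 → 78.5 |
| 68 | 26% vs 16% | 42.2 → 42.3 | 42.2 → 43.8 | 42.1 → 45.8 |

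**2. Baseline correction of continuous outcomes.**

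Let r be the baseline to follow-up correlation, assumed. Relative to the variance of follow-up scores:

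- covariance analysis: 1 − r²
- change scores: 2(1 − r)
- covariance analysis over change scores: (1 − r²)/[2(1 − r)] = (1 + r)/2

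At r = 0.5, covariance analysis has 25% less variance than follow-up scores (1 − 0.75) and 25% less than change scores (1 − 0.75). At r = 0.7 the reductions are 49% (1 − 0.51) and 15% (1 − 0.85).

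The conditional rule was simulated as adjusting only if the baseline difference is significant at 5%, with 136 per arm and an effect giving the plain t-test 80% power:

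| r | Always adjusted | Adjusted only on imbalance |
|---|---|---|
| 0.3 | 83% | 80% |
| 0.5 | 90% | 81% |
| 0.7 | 97% | 82% |

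At r = 0.7 the conditional rule's two-sided type I error falls to 3.6%.

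**3. Passages side by side.** Section 3 has four arms and 9.2 has two groups, so three contrasts with control or six pairwise contrasts could be meant. Section 9.2 lists VAS for baseline correction, while Table 1 has its first VAS in weeks 1-8. The summary likewise has pain scored weekly over the first 8 weeks and mentions no earlier score.

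**The case against.** **Detail for the analysis plan.** Naming covariates is often left to an analysis plan, and silence about strata does not exclude them. The Cox sentence in 9.2 shows that some adjustment is intended. This is fair as far as it goes, so it would be too much to say that the protocol rejects adjustment. But 4.4 and 9.1 do fix the primary tests, and the Cox sentence is in the secondary section and names no factor.

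**Small and in the safe direction.** A reader might infer that leaving out the strata inflates false positives. It does not; the test becomes conservative. At the planned 26% vs 11% and 136 per arm the loss is 0.1 to 0.7 points. This objection stands and limits the weight of the stratification part.

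**Baseline can be handled within a t-test.** A reader might infer that the named tests rule out baseline correction. They do not, since change scores can be tested, and against these the gain from covariance analysis is smaller (25% to 15%). The phrase might also mean baseline characteristics in general rather than the outcome's own baseline. On either reading the correction still depends on what is observed.

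**Wilcoxon test.** It could be read as replacing the comparison between arms. The preceding paragraph of 9.2 already covers that comparison, so a supplementary within-arm description is a fair reading.

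**Timing of the first VAS.** A reader might infer that it follows the first HBOT session. The protocol does not tie week 1 to the start of HBOT, so this is not established. It is established only that the score is not scheduled before randomisation.

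**Two groups.** This may be a slip that pairwise tests would satisfy. That is plausible, but the contrasts still need naming.

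**Conclusion.** The point holds at moderate weight. Two parts are inconsistencies in the protocol's own text: two-group wording in a four-arm trial, and a baseline correction listed for VAS with no baseline VAS scheduled. The conditional correction is a poor rule as stated. It concerns secondary outcomes only, and at assumed correlations of 0.5-0.7 it costs about 9 to 15 power points against always adjusting (90 − 81 and 97 − 82), if the trigger is a significant imbalance.

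The unstratified primary tests are valid but slightly inefficient. Under the assumed strata, one-sided error is about 4.9% to 3.7%. At 136 per arm the power loss is 0.5 to 4 points at 26% vs 16% and under 1 point at 26% vs 11%. At the interim's 68 per arm the loss at 26% vs 11% can reach about 2.4 points (78.5 − 76.1). These sizes rest on an equal split of the strata, on the chosen odds ratios and on fixed-sample pairwise tests. The log-rank test was not simulated. The sample size is not affected.

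**What to change.** - **Section 9.1.** Stratify the comparisons by minor amputation at entry and by centre, with small centres pooled by a rule set in advance. Use a Mantel-Haenszel test and risk difference at the interim, and a stratified log-rank test or Cox model at the end. Because 4.4 states its 5% and 15% thresholds for unadjusted percentages, say how the stratified interim estimate maps to them.
- **Section 9.2.** Replace the two-group wording with each HBOT arm against control. Use covariance analysis or a repeated-measures model with the outcome's baseline always included. Label any Wilcoxon test as within-arm description.
- **Table 1.** Add a VAS before randomisation. This is the most urgent change, since it cannot be made good after enrolment.

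The cost is analysis wording, a reconciliation with 4.4, and one extra baseline question. Centre by minor-amputation cells may be sparse with 68 per arm, and pooled centres no longer match the randomisation strata exactly.

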### **4.4 Sample size calculation**

The primary outcome is the probability of amputations after 12 months. The meta-analysis showed a 15% difference (11% vs. 26%; Brouwer 2020) of amputations between patients treated with HBOT and patients treated conservatively. The sample size calculation is based on a one-sided type I error of 5% and a power of 90% to control for a type 2 error. A

generalization of the power requirements for testing multiple active treatments to one control group was used as proposed by Dunnett (Dunnett 1984).

The critical values for continuation of a treatment arm are odds ratios of 0.76 and 0.352, which are in accordance with a drop in amputations from 26% to 21% and to 11%. If the difference is <5% the HBOT treatment arm is deemed futile, while a difference of 15% or higher is deemed superior. Based on these critical values the required number of patients in each group in each stage is 68, leading to a required maximum number of 544 patients. The sample size calculation is based on a generalization of Whitehead and Jaki (Whitehead 2009, Jaki 2019). Taking into account a possible loss to follow-up of 5%, we will need a total of (up to) 573 patients.

This leads to the following stopping rules and possible scenarios after the interim analysis (using the chi-square test for differences in percentages between the groups) (see figure 2 below):

- 1) If one of the HBOT treatment groups leads to a significantly less than 5% improvement in amputation rate as compared to controls (based on the expected 26% vs 21% difference, i.e. an OR of 0.76), then this treatment group will be discontinued as it is futile.
- 2) IF a HBOT treatment group proves to decrease amputation rate significantly by >15% (26% vs 11%; OR: 0.352) as compared to controls, then superiority of a treatment arm is proven and the trial will be discontinued as it has reached its aim. If more than one HBOT-treatment arm shows this superiority, the group with the lowest number of HBOT treatments is deemed superior.
- 3) If the HBOT group(s) show(s) minor improvements in amputation rate (between 5% and 15%) over control, then these groups will continue in the second stage of the trial.

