#### 7.1.1 Main study parameter/endpoint

- Major amputation rate (above ankle) and (major) amputation-free survival after 12 months of follow-up

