## 9. STATISTICAL ANALYSIS

All analyses will be conducted according to the intention-to-treat principle. Baseline characteristics are summarized with descriptive statistics. Differences between dichotomous variables (like the amputation rate) will be expressed as a risk differences and Numbers Needed to Treat or Harm. Statistical precision will be expressed as 95% confidence intervals. Differences between continuous variable will be expressed as difference in means. If outcome parameters are unevenly distributed, they will be expressed as medians and inter-quartile ranges.

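### The final analysis tests two unordered primary endpoints by log-rank without tying the tests to the one-sided 5% Dunnett error on which the trial was sized

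*Protocol*

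**What the plan says.** - **Sample size (4.4).** "The primary outcome is the probability of amputations after 12 months": one outcome, without the word 'major'. The error is one-sided 5%, the power 90%, and the method a Dunnett-type generalisation for several active arms against one control. This gives 68 patients per group per stage. Every HBOT arm with an improvement between 5 and 15 points goes on to stage 2, so up to three can reach the final analysis.
- **Endpoints (2 and 7.1.1).** The main endpoint is "Major amputation rate (above ankle) and (major) amputation-free survival after 12 months of follow-up". Section 2 and the Summary also list both. No order, alpha split or both-must-succeed rule is given.
- **Final analysis (9.1).** "At the final analysis, major amputation rates and AFS will also be estimated using Kaplan-Meier survival analysis". On how the arms are compared for these two endpoints, the section adds only that "differences between the groups will be analysed using the log-rank test".
- **Intervals (9).** "Statistical precision will be expressed as 95% confidence intervals". The same section expresses the amputation rate as a risk difference and number needed to treat (NNT).
- **Healing (9.2).** "Time to complete wound healing will be estimated using Kaplan-Meier survival analysis".

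**The concern.** The protocol controls error for one endpoint over three comparisons when it sets the sample size, but describes a final analysis with up to six comparisons (three arms, two endpoints). It does not say which of them decide the trial or at what threshold. Taken as it stands, the text would allow a claim of efficacy on whichever endpoint and arm looks favourable, at an error rate above 5%.

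The missing word 'major' adds to this. Section 1 attributes the 15-point reduction to major amputation and reports no effect on minor amputation, so 26% versus 11% belongs to major amputation, yet 4.4 speaks of amputations in general.

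A secondary matter is the estimator. An ordinary Kaplan-Meier curve for amputation alone censors deaths. Death is a competing event, so one minus Kaplan-Meier exceeds the proportion of patients actually amputated.

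**Working it through.** **1. The plan's own figures.**
- 68 x 4 arms x 2 stages = 544, and 544 / 0.95 = 572.6, so 573.
- Odds ratios: (0.21/0.79)/(0.26/0.74) = 0.757 and (0.11/0.89)/(0.26/0.74) = 0.352.
- A two-stage design with three arms against control, family-wise error 5% one-sided and power 90%, gives 67.3-67.5 per arm per stage with O'Brien-Fleming boundaries and the variance taken at the four-arm mean rate, hence 68. Other boundary and variance conventions give 55 to 81. The protocol states neither.

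**2. Critical values for one endpoint and three arms.** The Dunnett value for a single final look is 2.06: one-sided p = 0.0197 per arm, a two-sided interval of about 96.1%. The two-stage final boundaries are about 2.07 (O'Brien-Fleming), 2.19 (triangular) and 2.28 (Pocock). A 95% interval corresponds to 1.96 and an unadjusted one-sided 5% test to 1.645 (a 90% interval), so 95% matches neither level.

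**3. One endpoint, no adjustment.** Z_k = (e_k - e_0)/sqrt(2), with correlation 0.5 through the shared control; the error is P(max Z_k > c).

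| HBOT arms at final test | c = 1.645 | c = 1.96 |
|---|---|---|
| 1 | 5.0% | 2.5% |
| 2 | 8.8% | 4.5% |
| 3 | 11.8% | 6.2% |

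**4. Either endpoint suffices.** The protocol gives no mortality rate. Assume that 10-20% die without major amputation by 12 months, so AFS events in control are 36-46%. Endpoint correlation = sqrt(p1(1-p2)/(p2(1-p1))) with p1 = 0.26:
- p2 = 0.36: sqrt(0.26 x 0.64/(0.36 x 0.74)) = 0.79
- p2 = 0.46: sqrt(0.26 x 0.54/(0.46 x 0.74)) = 0.64

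If all three arms always continue, the error is 17-19% at 1.645 and about 10% at 1.96. A patient-level log-rank simulation (136 per arm, death hazards equivalent to 5-30% at 12 months) gives 15-18% and 8-11%.

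**5. With the futility rule in 4.4.** Simulate the global null: 26% in all arms, 68 per arm per stage, arms with under 5 points' observed improvement dropped at the interim. For simplicity the interim uses the 12-month rates. No arm continues in 55% of trials; all three continue in 7.5%.

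| Final analysis | c = 1.645 | c = 1.96 |
|---|---|---|
| One endpoint | about 10.5% | about 6% |
| Either endpoint | about 14% | about 8% |

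**6. Kaplan-Meier with deaths censored.** Let a be the true cumulative incidence of amputation and c that of death without amputation. With constant hazards, 1 - KM = 1 - exp(-L x a/(a+c)), where L = -ln(1-a-c). For a = 0.26 and c = 0.10: L = 0.446, and 1 - exp(-0.446 x 0.722) = 27.6%.

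| Assumed deaths | Timing of amputations | Control (true 26%) | HBOT (true 11%) | Difference (true 15) |
|---|---|---|---|---|
| 10% | constant hazards | 27.6% | 11.6% | 15.9 |
| 20% | constant hazards | 29.4% | 12.3% | 17.1 |
| 10% | 80% in months 0-3 | 26.7% | 11.3% | 15.4 |
| 20% | 80% in months 0-3 | 27.6% | 11.6% | 16.0 |

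The early pattern follows section 9.3, which says that most amputations occur within three months. The 80% share, and deaths spread evenly over the year, are assumptions.

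**The case against.** - **The tests are not called unadjusted.** Section 9.1 is silent on the threshold, 4.4 cites Dunnett and MAMS methods, and a SAP that is not shown may fix the boundary. This stands: a reader might infer that the plan has chosen unadjusted tests, but the text does not say so. What remains is that the protocol gives two unordered primary endpoints where it sized one, and does not link the final test to the stated error. The conflict between 4.4 and 7.1.1 lies within the protocol itself.
- **Threefold to fourfold inflation is a ceiling.** A reader might infer 17-19% as the plan's error rate. That needs all three arms to continue, a one-sided 5% test of each, and success on either endpoint. The futility rule in 4.4 lowers it to about 14%, or about 8% at 1.96.
- **The intervals are described as precision, not as a decision rule.** True, and 1.96 is stricter than 1.645. They still do not correspond to the design's error level.
- **'Major' can be inferred.** Sections 1, 2 (the aim) and 7.1.1 point to it. The omission in 4.4 is a matter of wording, but it falls in the sentence that defines the sized outcome.
- **The NNT is not shown to be biased.** A reader might infer this from the use of Kaplan-Meier. Section 9 bases the risk difference and NNT on the dichotomous rate, and 9.1 uses Kaplan-Meier 'also'. With complete follow-up, a crude 12-month proportion equals the cumulative incidence.
- **Nor is bias against HBOT in healing.** The protocol gives no healing or competing-event rates and does not say how deaths and amputations are coded. Such patients could be kept as never healed to month 12.

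**Conclusion.** The point holds as a mismatch between design and analysis. The trial is sized on one outcome at a one-sided 5% Dunnett-type error, while the final analysis names two primary endpoints with no order and a log-rank test with no link to that error. If either endpoint in any remaining arm counts as success, the final-analysis error is about 14% at one-sided 5% and about 8% at 1.96. This assumes 10-20% mortality and dropping on the observed difference; 17-19% and about 10% apply only if all three arms always continue. With one surviving arm and one endpoint there is no inflation at the final test.

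The Kaplan-Meier point is real but small. If deaths are censored, the amputation difference is overstated by about 0.5-1 point with early amputations, or 1-2 points with constant hazards, at 10-20% assumed mortality. Kaplan-Meier for AFS has no such problem, because death is an event there.

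**What to change.** 1. Make major amputation at 12 months the single primary endpoint, and use 'major' in sections 2, 4.4 and 9.1.
2. Test AFS for an arm only after major amputation has succeeded for that arm.
3. In 9.1, compare each remaining HBOT arm with control against the final critical value of the MAMS design that produced 68 per arm. State that boundary; it lies at about 2.07-2.28 depending on its shape. Give intervals at the matching level for these comparisons.
4. Keep Kaplan-Meier for AFS. Report time to major amputation and time to healing as cumulative incidence (Aalen-Johansen), with death, and for healing also major amputation, as competing events.

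The cost is protocol and SAP wording. AFS loses its equal primary status. An alpha split or a formal both-must-succeed rule would also remove the ambiguity. But a split raises the single-look Dunnett value from 2.06 to 2.35, and the protocol gives no power for AFS if both must succeed. The fixed order avoids both and needs no further patients, since the design's boundary is already part of the calculation behind 68.
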